## **14 SAFETY ANALYSIS**

The Safety Population will be assessed for AEs, SAEs, AEs leading to discontinuation/withdrawal, DLTs, AESIs, physical examination, vital signs, ECGs, and clinical laboratory tests. All analyses of the safety data will be performed by adult equivalent dose levels. Urinalysis, psychiatric evaluations, and concomitant medications will be presented in listings only.

### **14.1 Adverse Events**

All AE verbatim terms reported on the eCRF will be coded using the Medical Dictionary for Regulatory Activities (MedDRA® version 24.1).

All reported AEs (including non-TEAEs) will be listed. Separate listings will be provided for SAEs, TEAEs leading to study drug discontinuation, DLTs, AESIs, and AEs related to COVID-19.

All TEAE counts will be by enrollment experience (re-enrollers will be counted once per enrollment) and not by event. Subjects reporting the same TEAE on multiple occasions will have, the highest severity (severe  $>$  moderate  $>$  mild) or study drug relationship (related  $>$  probable  $>$  possible  $>$  unlikely  $>$  unrelated) recorded for the event in each enrollment experience will be summarized. All AE summary tables will display the number and percentages of subjects per enrollment experience reporting TEAEs, unless otherwise specified.

An overall summary of AEs will be reported and will include the number and percentage of subjects experiencing any AEs, SAEs, TEAEs, TEAEs by maximum severity (highest toxicity grade), study drug related TEAEs by maximum severity (highest toxicity grade), study drug related SAEs, DLTs, AESIs, TEAEs leading to study drug discontinuation, and TEAEs leading to deaths.

The number and percentage of subjects experiencing each TEAE, study drug related TEAE, and SAEs will be displayed in summary tables by adult equivalent dose levels as well as by cohort according to system organ class and preferred term. Tables including only preferred term summarized by adult equivalent dose levels as well as by cohort for the number and percentage of subjects experiencing each TEAE will be presented.

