Cohort 4 (adults) and Cohort 6 (11-17 years) will initiate concurrently at 200mg BID (200 mg BID has been previously evaluated in adults in study SPR001-201). Upon completion of the 4-week dosing on 4 sentinel participants from Cohorts 4 and 6 combined, the DMC will assess safety data and provide recommendations on continued dosing. If the DMC assesses it to be safe to proceed to a higher dose, Cohort 5 (adults) may be initiated at 300mg or 400mg BID and Cohort 7 (2-10 years) may be initiated at 200mg BID. Following the completion of the 4-week dosing periods for Cohorts 5 and 7, the DMC will review safety data from 4 sentinel participants and offer recommendations on whether to proceed to Cohort 8 (11-17 years) and at what dose (300mg or 400mg BID). Following completion of Cohort 8, the DMC will review the safety data from 4 sentinel participants and provide a recommendation on whether to proceed with Cohort 9 and at what dose (300mg or 400mg BID) ([Table 1](#)).

All cohorts including doses above 200 mg BID will be adaptive, so that the determination to initiate a cohort, and at what dose, may be determined by the Sponsor, within the guidelines of the protocol, based on recommendations by an independent Data Monitoring Committee (DMC) and emerging safety and exposure data. Individual and study stopping criteria will further ensure safety of the participants.

Please see [Section 3](#) for details on Study Design and [Section 6](#) for details on stopping criteria.

Study Conduct: There are 7 scheduled visits over approximately 18 weeks for Cohorts 1 to 3; and 5 scheduled visits over approximately 10 weeks for Cohorts 4 to 9. Visits are detailed in the Schedule of Activities. All visits should be performed on site, but alternative arrangements may be used if an on-site visit is not feasible. Adverse events and concomitant medications will be collected at each visit.

Any participant enrolled under protocol amendment 3 may be re-consented to protocol amendment 4 and receive the 12-week treatment course; however, because they will have already contributed PK data, they will not be required to have blood draws for tildacerfont concentration on Days 1 and 14 between 0.5 to- 1.5 hours and between 3 to 5 hours post dosing. Additionally, any participant enrolled under amendment 4 (or any other tildacerfont study) may be re-consented and enrolled under protocol amendment 5.

Please see [Section 3](#) and [Section 10.2](#) for details on Study Conduct.

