For these cohorts, the study will last approximately 18 weeks including a 2-week Screening Period, a 12-week Treatment Period and a Safety Follow-up visit 30 days after the last dose of study drug (during the Treatment Period). Participants may continue in an extension period upon completion of the 12-week Treatment Period. If participants enroll in the extension study after the 12-week Treatment Period, the Safety Follow-up Visit will occur 30 days after the last dose in the extension.

Dosing will begin in Cohort 1 with participants 11- to 17- years of age dosing at the adult equivalent of 50 mg QD. Cohort 2 will continue in the same 11– to 17-year-old age group but dosing at 200 mg QD. Cohort 3 will enroll participants 2-to 10-years of age but dose no higher than Cohort 2. If safety concerns are identified in the Cohort 1 participants, an interim dose Cohort 1a may be initiated prior to proceeding to Cohort 2 dosing.

Cohort 1 will include up to approximately 5 participants who will receive a tildacerfont dose that is equivalent to the adult dose of 50 mg. Data from the first 2 participants will be considered sentinel and will inform a safety review by an independent DMC. After reviewing the first 2 weeks of data from the sentinel participants, the DMC will make one of three recommendations regarding continuing enrollment:

- 1) If data suggest the dose was well-tolerated by the sentinel participants, Cohort 2 (200 mg equivalent) will be initiated.
- 2) If a safety concern is identified, for example, a sentinel participant experiences an individual stopping criterion or a suspected unexpected serious adverse reaction (SUSAR), the DMC may withhold their recommendation until additional safety data are available from the additional 3 participants in Cohort 1.

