5.1. Treatment Administration

Participants will be treated with oral tildacerfont QD for 12 weeks (Cohorts 1 to 3) or BID for 4 weeks (Cohorts 4 to 9).

Pediatric age and weight-based tildacerfont dose levels are defined in [Table 2](#). For each dose level, the amount of study drug that a participant will receive will depend on the participant's age and body weight at Screening according to [Table 2](#).

Cohort 1 will be dosed at the equivalent of the adult 50 mg dose. Cohort 2 will receive the equivalent of the adult dose of 200 mg. If needed based on a safety concern in participants in Cohort 1, an interim dose Cohort 1a may be included. Cohort 3 will dose no higher than Cohort 2 (or Cohort 1a) but enroll up to approximately 10 participants in the younger age group of 2- to 10- years.

Cohorts 4, 6, and 7 will dose at the 200 mg adult dose equivalent BID; and Cohort 5, 8 and 9 will dose at up to 400 mg adult dose equivalent twice per day. Based on DMC recommendation and Sponsor decision, taking into account all available safety and exposure data, Cohorts 5, 8 and 9 may be initiated at 300mg adult equivalent BID for approximately 5 participants each, and then another approximately 5 may be enrolled in each at 400mg adult equivalent BID after DMC review.

Table 2. Tildacerfont Dose Levels and Pediatric Weight-Based Dosing

Weight at Screening (kg)	50 mg QD adult equivalent dose	100 mg QD adult equivalent dose	200 mg QD or BID adult equivalent dose	300mg BID adult equivalent dose	400 mg BID adult equivalent dose
Age group: 2- to 5-years					
13 to 14.1	25	50	75	100	150
14.1 to <21.2	25	50	75	100	150
21.2 to <26.1	25	50	100	150	200
26.1 to <31.8	25	75	100	150	200
31.8 to <33.9	25	75	150	150	300
≥33.9	50	100	150	150	300
Age group: 6- to 10-years					
20 to <23.7	25	50	75	100	150
23.7 to <29.9	25	50	100	150	200
29.9 to <35.5	25	75	100	150	200
35.5 to <39.2	25	75	150	200	300
39.2 to <47.5	50	100	150	200	300
≥47.5	50	100	200	300	400
Age group: 11- to 17-years					
26 to <30.5	25	50	75	100	150
30.5 to <39.2	25	50	100	150	200
39.2 to <45.7	25	75	100	150	200
45.7 to <53.4	25	75	150	200	300
53.4 to <61	50	100	150	200	300
≥61	50	100	200	300	400

Abbreviations: QD=once daily.

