8.3.4. Safety Analyses

The Safety Population will be used for all safety analyses. Safety data will be listed by participant and summarized by adult equivalent dose levels (50, 100, 200 mg QD; and 200 mg, possibly 300 and/or 400 mg BID) using the frequency of event or descriptive statistical summaries, as appropriate. Listings and summary tables will be provided for AEs, clinical laboratory tests, vital signs, and ECG data. Urinalysis, psychiatric evaluations, concomitant medications, and physical examinations will be presented in listings only.

A DMC will review accumulating safety information by cohort. Refer to [Section 9.4.4](#) for information on the DMC.

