### 6.1 Objectives and Endpoints

#### 6.1.1 Primary

The primary objective is to evaluate the safety of tildacerfont in pediatric (ages 2 to 17 years old) and adult subjects ( $\geq 18$  years old) with classic congenital adrenal hyperplasia. The primary endpoint is the occurrence of AEs and SAEs as described in [Section 5.3.1.1](#).

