### *9.4.18 Adverse Events*

AEs are any untoward medical occurrence in a subject participating in a clinical trial with onset date from the signing of the informed consent/assent until the end of the follow up period.

TEAEs are defined as any AEs, regardless of relationship to study drug, which have an onset or worsening in severity on or after the first dose of study drug until 30 days after the final dose of study drug (Follow-up visit). For AEs that occur on the date of the first dose of study drug, the time of onset (before or after intake of study drug) will be specified and used for comparison. If a subject discontinues study drug but remains in the study, AEs with onset date after 30 days of last dose of study drug until the end of the follow up period will be considered post-treatment adverse events.

Related TEAEs are those reported by investigators as possibly related, probably related, or definitely related to the study drug.

AESIs are events that do not meet SAE criteria but must be monitored on an ongoing basis as defined in the Study Protocol Section 7.2.8 and identified in the AE eCRF page.

Serious AEs (SAEs) are defined in the Study Protocol Section 7.2.6 and identified in the AE eCRF page.

Dose-limiting toxicities (DLTs) are defined as a Common Terminology Criteria for Adverse Events (CTCAE) Grade 3 or higher TEAE that is also considered at least possibly related to study drug.

Suspected unexpected serious adverse reactions is an AE that is serious, related to study drug, and is not expected in the targeted disease (classic CAH).

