The Study Protocol Section 8.3.4.1 states that “Using dosing data, estimates of exposure to tildacerfont will be summarized.” However, due to limitations in the collection of exposure and drug accountability data in this study, it is not possible to estimate tildacerfont exposure without making assumptions about the last dose date of the 12-week treatment period, the number of tablets dispensed, and the strength of the tablets dispensed. Therefore, information about exposure will only be listed on an individual basis as described in [Section 12.1](#).

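### Crude TEAE percentages by dose level (SAP 14.1) are not comparable between the QD and BID levels, because planned time at risk differs about two- to threefold

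*SAP*

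**What the plan says.** Safety is the primary objective, and SAP 6.1.1 states: "The primary endpoint is the occurrence of AEs and SAEs".

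- **Statistic.** SAP 14.1 plans counts and percentages: "subjects experiencing each TEAE, study drug related TEAE, and SAEs will be displayed in summary tables by adult equivalent dose levels", and the same tables by cohort. SAP 9.1 takes the number of subjects dosed as the denominator.
- **Columns.** Protocol 8.3.4 and SAP 5.3.1 place QD and BID levels in one summary: "summarized by adult equivalent dose levels (50, 100, 200 mg QD; and 200 mg, possibly 300 and/or 400 mg BID").
- **Treatment time.** Protocol 5.1: "Participants will be treated with oral tildacerfont QD for 12 weeks (Cohorts 1 to 3) or BID for 4 weeks (Cohorts 4 to 9").
- **Counting window.** SAP 9.4.18 counts events with onset or worsening "on or after the first dose of study drug until 30 days after the final dose of study drug".
- **Extension.** For participants who continue, Protocol 3.1 says "the Safety Follow-up Visit will occur 30 days after the last dose in the extension". SAP 4 sends the extension analysis to a separate SAP. Neither document says on what date a continuing participant's events stop counting in the main-period tables.
- **Exposure.** Protocol 8.3.4.1 promises a summary of exposure. SAP 15 withdraws it: "information about exposure will only be listed on an individual basis".

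The SAP contains no rate per person-time, no common-window table and no caveat about duration.

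**The concern.** The probability of at least one event grows with time observed. Every BID column has a shorter window than every QD column, so a crude percentage mixes the effect of the regimen with the length of observation. The mixing runs in one direction: it lowers the BID percentages relative to QD. The by-cohort tables do not help, because Cohorts 1 to 3 are all 12-week cohorts and Cohorts 4 to 9 are all 4-week cohorts.

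The study has no control group and plans no between-dose test, so these percentages are the primary result as it will be reported. A reader who sees similar or lower percentages in the BID columns could take them as reassurance about the higher daily doses when part of the difference is observation time. Without the exposure summary, no table shows the reader how long each column was observed.

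**Working it through.** **Check against the plan's own figures.** The synopsis (Study Conduct) gives "7 scheduled visits over approximately 18 weeks for Cohorts 1 to 3; and 5 scheduled visits over approximately 10 weeks" for Cohorts 4 to 9. With 2 weeks of screening and 30 days of follow-up:

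- Cohorts 1 to 3: 2 + 12 + 30/7 = 18.3 weeks.
- Cohorts 4 to 9: 2 + 4 + 30/7 = 10.3 weeks.

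Both agree with the stated lengths, so the inputs are read correctly.

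**Time at risk for TEAEs**

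| Window | QD | BID | Ratio |
|---|---|---|---|
| Treatment only | 84 days | 28 days | 3.0 |
| Treatment + 30 days, stopping at end of treatment | 114 days | 58 days | 1.97 |

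For participants who enter the extension the window is undefined, because no cut-off is given. If the tail were counted in one regimen but not the other, the ratio could be 84/58 = 1.45 or 114/28 = 4.07.

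**Effect at equal hazards.** The documents give no AE rates, so the risks below are assumptions. With a constant hazard and BID-window risk p, the QD percentage is 1 − (1 − p)^r, where r is the ratio above.

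| Assumed BID percentage | QD, r = 114/58 | QD, r = 3 |
|---|---|---|
| 20% | 35.5% | 48.8% |
| 30% | 50.4% | 65.7% |
| 40% | 63.4% | 78.4% |

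For example, 1 − 0.7^(114/58) = 50.4% and 1 − 0.7^3 = 65.7%.

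**If the BID hazard were truly doubled.** The BID percentage becomes 1 − (1 − p)^2, which at p = 30% is 51.0%. Against QD that is 51.0% v 50.4% with the tail window (the doubling is hidden), or 51.0% v 65.7% on treatment only (BID looks better). Equal columns need a true rate ratio of about 1.97 or 3.0 respectively.

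**Front-loaded events.** With a Weibull hazard of shape k and a QD percentage of 50%, the BID percentage is 1 − 0.5^((t_BID/t_QD)^k). For k from 0.7 down to 0.3 this gives 35% to 43% (114/58 days) or 27% to 39% (84/28 days). With a constant hazard it is 29.7% or 20.6%. The gap shrinks but remains.

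**Small groups.** These are exact binomial probabilities, with equal hazards and QD at 50%, that the observed BID percentage falls below the QD percentage:

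- 15 v 15 participants: 0.83 (114/58 days) or 0.94 (84/28 days).
- 5 v 5 participants: 0.64 or 0.76.

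With a true rate ratio of 3, the 114/58-day window and 15 v 15, BID is lower in only 15% of comparisons.

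**The case against.** The other side has several fair points.

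- **The treatment durations are not the TEAE window.** For participants who stop at end of treatment the ratio is about 2, not 3. This stands, and both windows are shown above for that reason.
- **A reader might infer that higher doses will look safer by design.** The documents do not support that. The 50, 100 and 200 mg QD levels share 12 weeks, and the 200, 300 and 400 mg BID levels share 4 weeks, so comparisons within each regimen are sound. Between regimens this is a bias, not a certain result: a large enough true effect, or chance in groups of 5, can reverse it.
- **A reader might infer that a doubled BID hazard would still show a lower percentage.** That is so only if the tail is excluded. Under the SAP's own window the columns come out level.
- **A reader might infer that escalation in children rests on these tables.** It does not. Protocol 3.1 and 3.1.1 base cohort decisions on DMC review of safety data from sentinel participants.
- **The tables are descriptive and SAP 10.5 calls the study exploratory.** True, but SAP 14 chose dose level as the organising column, and side-by-side percentages invite comparison whether or not a test is run.
- **Planned durations are stated, and AEs and dosing are listed by subject.** A determined reader could partly adjust. Listings do not replace a matched summary of the primary endpoint. Table conventions sit in a separate mock-shell document (SAP 9), which was not available for this review.

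**Conclusion.** The concern holds for QD-versus-BID comparisons only. The plan as written biases them toward BID looking safer, with planned time at risk about 2 times longer for QD with the 30-day tail and 3 times longer on treatment. Under an assumed constant hazard, equal true rates show as about 30% for BID against 50% or 66% for QD. A true rate ratio of about 2 to 3 would only bring the columns level.

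The size rests on assumed event rates and on the shape of the hazard. Front-loaded events make the gap smaller, and small groups make any single comparison noisy. The direction of the bias and the absence of any correction in the SAP do not depend on those assumptions. Severity: should-fix, because the tables are descriptive and do not drive the DMC's decisions, but they do carry the primary endpoint.

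**What to change.** In SAP 14.1:

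1. Keep the planned full-window tables by dose level and by cohort, with a footnote stating the observation window behind each column.
2. Add dose-level tables of subjects with TEAE onset in the first 28 days after first dose, for all cohorts. Flag participants who stopped early. Use these tables for any QD-versus-BID reading.
3. Show later TEAEs separately for both regimens, from after Day 28 to the end of the TEAE window. The Day-28 tables must be added, not substituted. Restricting every between-dose table to 28 days would drop BID events from Day 29 to about Day 58, and with them any delayed toxicity at the BID levels.
4. Add first-event rates per person-week from first dose to the EOT or ET visit, with numerator and time at risk both cut at that visit. Apply the same cut-off to participants who enter the extension.

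The Day-28 tables need only first-dose and AE-onset dates, so the last-dose-date limitation in SAP 15 does not block them. The rates use scheduled visit dates instead of last dose dates. At full enrolment the planned on-treatment time is 25 × 12 = 300 person-weeks for QD and 45 × 4 = 180 for BID.

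Cost: a few extra tables, a footnote and one SAP paragraph. No new data collection is needed.

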## **14.2 Clinical Laboratory Evaluation**

Laboratory parameters chemistry, hematology, coagulation, and thyroid panel will be displayed in summary tables by cohort and scheduled time point and will include both observed values and change from baseline values. As applicable, a summary of laboratory parameters will also be displayed in a shift table of baseline values relative to normal ranges (low, normal, high, missing). Subject-level listings for urinalysis and all laboratory parameters (see [Table 12](#)) will be provided. A separate listing will include abnormal clinical laboratory test results. In addition, subjects concurrently meeting the following Hy's law criteria at any assessment date will be identified and listed:

- Alanine aminotransferase (ALT)  $> 3 \times$  ULN
- Aspartate aminotransferase (AST)  $> 3 \times$  ULN
- Total bilirubin (TBL)  $> 2 \times$  ULN

## **14.3 Vital Signs**

Pulse rate, respiratory rate, temperature, including baseline values and change from baseline values, will be summarized with descriptive statistics by cohort and scheduled time point. All vital signs parameters will be listed.

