7.1.2. Vital Signs

Vital signs consist of systolic and diastolic blood pressure, pulse rate, respiration rate, and body temperature. The participant should ideally have an empty bladder. Vital signs will be measured as specified in the Schedule of Activities ([Appendix 1](#) and [Appendix 2](#)) and as clinically indicated.

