7.2.8. Adverse Events of Special Interest

AESIs are those AEs (independent of seriousness criteria) that are of specific concern to this study and for which ongoing monitoring and communication with the Investigator and Sponsor may be appropriate. These events will be reported on the SAE Report Form, allowing for the collection of additional information, as warranted. The following may be considered AESIs for this study:

- Significant liver chemistry changes that do not satisfy study drug stopping rules (see [Section 6.1.2](#)). Cases of Hy's Law should be reported as an AESI and SAE.
- Suicidality as indicated by responses on the C-SSRS (see [Section 6.1.5](#) regarding study stopping criteria).
- Depression or anxiety that is moderate or severe (CTCAE Grade 2 or higher), as assessed by the Investigator (see [Section 6.1.6](#) regarding study drug stopping criteria for depression or anxiety). This will be reported as an AESI and if seriousness criteria are met, reported as an SAE.
- Adverse events of adrenal insufficiency are considered AESIs and will be reported on a separate Adrenal Insufficiency Form. Additionally, symptoms of adrenal insufficiency will be reported as SAE if they necessitate parenteral GC administration by a health care professional and two of the following criteria occur or are met: hypotension (systolic blood pressure <90 mmHg); nausea or vomiting; severe fatigue; documented hyponatremia, hyperkalemia, or hypoglycemia. If hospitalization was required or the event of adrenal insufficiency is deemed to be an important medical event, life-threatening, or results in a persistent or significant disability/incapacity or death, it should also be reported as an SAE.
 - For SAEs of adrenal insufficiency, records from the office of the health care provider, emergency facility or hospital should be obtained as source documents to provide the following information:
 - Was stress dosing employed prior to the adrenal insufficiency event? If yes, what were the GC dose and duration of dosing and the cause for stress dosing prior to seeking medical attention?
 - What type, dose and route of parenteral GC was administered and the duration of administration?
 - What concomitant medications were administered?
 - What clinical laboratory results are available?
 - What AEs occurred?
 - What was the duration of stay if admitted to the hospital?
 - What was deemed to be the inciting factor leading to adrenal crisis?

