8.3.4.4. Vital Signs Data

Vital signs data will be summarized within appropriately defined categories in terms of observed values (by time point), changes from baseline (by time point), and counts and percentages.

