## 4 PURPOSE OF THE ANALYSIS PLAN

This statistical analysis plan (SAP) pre-specifies the statistical analysis methods for supporting the completion of a clinical study report (CSR) of Study SPR001-205 for tildacerfont, an investigational drug candidate designed to treat classic congenital adrenal hyperplasia (CAH). This SAP will be used to analyze the safety, efficacy, and pharmacodynamics (PD) data collected during the study. The planned analyses identified in this SAP may be included in regulatory submissions and/or future manuscripts.

The analysis methods described in this plan are considered *a priori*, in that they have been defined prior to clinical database lock. Exploratory analyses that are not defined in this SAP may be performed to support the clinical development program. Any post-hoc or unplanned analyses that are performed for the CSR, but not defined in this SAP, will be documented in the CSR. Changes from the planned analyses are described in [Section 15](#). Should the SAP and the protocol be inconsistent with respect to any further planned analyses, the language of the SAP is governing.

The analysis of pharmacokinetic (PK) concentration data and its parameters will be documented separately. The data analysis for the open label extension period will be covered in a separate SAP.

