#### *5.3.1.3 Vital Signs*

The following vital signs will be assessed: blood pressure (systolic and diastolic; mmHg); pulse rate (beats per minute); respiration rate (breaths per minute); and body temperature (°C). Vital signs will be obtained at all clinic visits as shown in [Table 8](#), [Table 9](#), [Table 10](#), and [Table 11](#).

Total body weight (kg) will be collected at each visit. Height (cm) will be measured at Screening and every 6 months thereafter (for those enrolled in the extension). From these assessments, body mass index (BMI; kg/m^2) and body surface area (BSA; m^2) will be calculated.

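### SAP 14.3 leaves blood pressure in a listing with no summary table, contrary to protocol 8.3.4.4 and SAP 5.3.1, and the departure is not declared

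*SAP*

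**What the plan says.** Both documents treat blood pressure as a vital sign. Protocol 7.1.2 says: "Vital signs consist of systolic and diastolic blood pressure, pulse rate, respiration rate, and body temperature". SAP 5.3.1.3 puts it first in its own list and says vital signs are obtained at all clinic visits.

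Both documents also promise summaries. Protocol 8.3.4 and SAP 5.3.1 each commit to listings and summary tables for vital signs. Protocol 8.3.4.4 adds the content: "Vital signs data will be summarized within appropriately defined categories in terms of observed values (by time point"), followed by changes from baseline and by counts and percentages.

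SAP 14.3 is narrower. It reads "Pulse rate, respiratory rate, temperature, including baseline values and change from baseline values, will be summarized with descriptive statistics", by cohort and scheduled time point. It then adds: "All vital signs parameters will be listed". SAP 14 says that all safety analyses will be done by adult equivalent dose level. SAP 15, which records departures from the protocol's analyses, mentions neither blood pressure nor vital signs.

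**The concern.** A programmer working from SAP 14.3 would produce tables for pulse, respiration and temperature and would list blood pressure. The study would then report no observed-value or change-from-baseline table for either pressure, although safety is its primary objective. A reader would have to find any drift in pressure with dose or time by scanning individual records.

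The protocol gives blood pressure some specific relevance. Section 7.2.8 makes adrenal insufficiency an adverse event of special interest. Among the criteria for reporting its symptoms as serious is "hypotension (systolic blood pressure <90 mmHg"). The background section also links the salt-wasting form of the disease to hypotension. The change is undeclared as well, although protocol 8.3.1 expects any change to its analyses to be pre-specified in the SAP.

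**Working it through.** The plan gives no figure to reproduce. The check is a comparison of texts plus a count.

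**1. Variables collected and summarised.**

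| Variable | Defined as a vital sign (protocol 7.1.2, SAP 5.3.1.3) | Summarised in SAP 14.3 | Listed in SAP 14.3 |
|---|---|---|---|
| Systolic pressure | yes | no | yes |
| Diastolic pressure | yes | no | yes |
| Pulse rate | yes | yes | yes |
| Respiration rate | yes | yes | yes |
| Temperature | yes | yes | yes |

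So 5 − 3 = 2 variables have no summary. Counting blood pressure as one vital sign, it is 1 of 4.

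**2. Is the omission a deliberate restriction?** The two sentences of 14.3 differ in scope: one names three parameters to summarise, the next lists all of them. Taken literally, blood pressure is listing only. No reason is given in 14.3 or in SAP 15. SAP 15 does declare changes to the PD set, the elevated-baseline set, 11-ketotestosterone, GC dosing frequency and exposure.

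**3. Does another SAP sentence restore the table?** SAP 5.3.1 promises vital-sign summary tables, and SAP 5.3.1.3 counts blood pressure as a vital sign. Read together they imply a blood-pressure table, which 14.3 does not provide. The SAP therefore conflicts with itself as well as with the protocol. SAP 4 provides that where SAP and protocol differ on planned analyses, "the language of the SAP is governing". That clause ranks the SAP above the protocol but does not rank one SAP section above another.

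**4. Other gaps in the same section.** Section 14.3 has none of the categorical counts and percentages that protocol 8.3.4.4 asks for, for any vital sign. It also summarises by cohort only, whereas SAP 14 says dose level.

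**5. How many participants have protocol-driven GC changes in the main treatment period?** From the cohort table:
- Cohorts 1, 1a, 2 and 3: 5 + 5 + 5 + 10 = 25. The A4 algorithm acts on Week 4 and Week 8 results, so changed doses can affect pressures mainly at Weeks 8 and 12. The algorithm can reduce, maintain or increase the dose.
- Cohorts 4 to 9: 5 + 10 + 5 + 5 + 10 + 10 = 45. Protocol 3.1 allows no GC adjustment during their 4 weeks.
- Total: 25 + 45 = 70. The extension is left to a separate SAP.

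The missing table concerns up to 70 participants. The argument from GC reduction concerns at most 25 of them.

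**6. Size of the groups to be summarised.** A cohort has 5 to 10 participants. A dose level can pool more: 200 mg BID covers Cohorts 4, 6 and 7, which is 5 + 5 + 5 = 15.

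**The case against.** The strongest reply is that little is lost. Blood pressure is collected and every value is listed. With 5 to 10 participants in a cohort, a listing can be read directly and a mean change is imprecise. The primary endpoint is adverse events and serious adverse events, not vital-sign means. Under SAP 14.1, hypotension reported as treatment-emergent would be tabulated by dose level and cohort, and events of special interest and serious events are counted in the overall summary. Protocol 1.3 reports no cardiovascular concern from vital signs or ECGs to date. Given SAP 5.3.1, the wording of 14.3 may be a drafting slip, and the table shells, which are kept in a separate document, might already contain the rows.

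Most of this stands, and it limits the weight of the point. It does not remove it. Small cohorts are equally small for pulse, respiration and temperature, which 14.3 does summarise. Adverse-event tables show only what an investigator reported. Shells that cannot be seen do not correct the governing text.

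A reader might also infer more than the documents support:
- That blood pressure is lost from the study. It is not; only the summary is missing.
- That hypotension marks the study's main safety risk. Protocol 7.2.8 gives adrenal insufficiency as one of several events of special interest, beside liver changes, suicidality, and depression or anxiety. Low systolic pressure is one of several criteria; two are needed, together with parenteral GC given by a health professional.
- That GC is being lowered in all participants. The count above shows otherwise.
- That participants below 90 mmHg should be counted at every age. That value belongs to a rule for reporting serious events, and nothing in the documents supports it as a summary category from age 2 to adulthood.

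**Conclusion.** The point holds as an undeclared gap in the safety output. SAP 14.3, followed literally, yields no summary of systolic or diastolic pressure, contrary to protocol 8.3.4 and 8.3.4.4 and to SAP 5.3.1. The direct consequence is narrow: a shift in pressure not reported as an adverse event would be in no summary table. No conclusion about the drug is shown to be wrong, and no bias can be quantified.

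This is more than a wording matter because the operative section, not just a description, omits the variable, and because safety is the primary objective. It rests on two assumptions: that programmers follow 14.3 as written, and that the unseen table shells do not add the rows. It should be corrected before database lock.

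**What to change.** Amend SAP 14.3 to add systolic and diastolic blood pressure to the parameters summarised: observed values and change from baseline at each scheduled time point, by cohort and, as SAP 14 states, by adult equivalent dose level. Add the counts and percentages that protocol 8.3.4.4 calls for, in categories the sponsor defines in advance and suits to age. If the omission was intended, declare and justify it in SAP 15 and reconcile SAP 5.3.1 with it.

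The data are already collected and listed. The cost is one line in the SAP, a short definition of categories, and extra rows in an existing table.
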